#### 5.4.2 HANDLING OF PARTICIPANT WITHDRAWALS OR TERMINATION

Every effort will be made to continue follow-up of withdrawn or terminated subjects or subjects who discontinue the intervention but remain in the study for follow-up, especially for safety and efficacy study endpoints. Every effort will be made to undertake protocol-specified safety follow-up procedures to capture AEs, serious adverse events (SAEs), and unanticipated problems (UPs).

### 5.5 PREMATURE TERMINATION OR SUSPENSION OF STUDY

This study may be temporarily suspended or prematurely terminated if there is sufficient reasonable cause. Written notification, documenting the reason for study suspension or termination, will be provided by the suspending or terminating party to investigator, the investigational device sponsor and regulatory authorities. If the study is prematurely terminated or suspended, the principal investigator (PI) or sponsor will promptly inform the IRB and will provide the reason(s) for the termination or suspension.

Circumstances that may warrant termination or suspension include, but are not limited to:

- Determination of unexpected, significant, or unacceptable risk to participants

- Demonstration of efficacy that would warrant stopping
- Insufficient compliance to protocol requirements
- Data that are not sufficiently complete and/or evaluable
- Determination of futility

Study may resume once concerns about safety, protocol compliance, data quality are addressed and satisfy the sponsor, IRB and/or regulatory authorities.

## 6 STUDY DEVICE

### 6.1 STUDY DEVICE(S) AND CONTROL DESCRIPTION

#### 6.1.1 ACQUISITION

The investigational device will be shipped to the investigative site directly from the sponsor. Training on the use of the device will be provided by the sponsor. The investigative site will not perform any treatments until all regulatory and IRB approvals are in place and the site has received training for both the device and the study.

#### 6.1.2 DEVICE SPECIFIC CONSIDERATIONS

The Venus LED device is intended to be used in aesthetic and cosmetic procedures. The device consists of a console and an applicator belt that delivers the treatment LED to the patient's skin.

The clinician is able to control the settings from the user interface (LCD GUI) display on the main console. The available settings for this applicator is:

- Power density up to 1.4 W/cm^2

The duration of exposure and frequency of exposure to the LED will be one 24 minute session.

### 6.2 STUDY DEVICE ACCOUNTABILITY PROCEDURES

The device will be shipped to the site by the sponsor. The device will be labeled as an investigational device and will require protocol and device training from the sponsor.

## 7 STUDY PROCEDURES AND SCHEDULE

### 7.1 STUDY PROCEDURES/EVALUATIONS

#### 7.1.1 STUDY SPECIFIC PROCEDURES

The following procedures and evaluations will be done as part of the study:

Demographics

Medical / surgical history (obtained by interview or from medical records)

Assessment of eligibility

Vital signs [including height (visit 1 only), weight, temperature, respiratory rate, heart rate and blood pressure] assessed at every study visit  
Administration of questionnaires and scales for patient-reported outcomes  
Temperature measurements  
Adverse event recording  
Concomitant medications

## 7.2 LABORATORY PROCEDURES/EVALUATIONS

### 7.2.1 CLINICAL LABORATORY EVALUATIONS

For women of child-bearing potential, urine pregnancy test to be performed according to local site standards within 24 hours of study intervention and results must be available prior to administration of the treatment.

## 7.3 STUDY SCHEDULE

### 7.3.1 SCREENING

#### **Screening Visit**

If the subject meets the preliminary study criteria the study doctor, and/or his/her designee, will obtain an informed consent from the subject, clearly indicating his/her understanding of the requirements and possible risks involved with study participation and other applicable treatment options.

During the first visit, the study investigator, and/or his/her designee, will screen the subject for eligibility to participate in the clinical study using the inclusion/exclusion criteria. A urine sample for the pregnancy test will be obtained for female subjects of child-bearing potential. During screening, the study doctor will review the subject's medical/surgical history, and examine the target treatments areas to ensure they meet the study criteria. The subject will complete screening and the treatment will be scheduled. Treatment may be performed on the same day the subject was enrolled if the result of the urine pregnancy test is available and negative.

During the first visit, the investigator will ask women of child-bearing potential for the date of their last period, if not applicable the investigator shall inquire about the form of contraceptive they use to confirm they meet the inclusion criteria.

#### **Pre-Treatment**

Subjects will be instructed to avoid sun exposure of the target treatment areas for at least six weeks before treatment and to use broad spectrum sunscreen of no less than 30 SPF daily, replenishing it as often as needed throughout the course of the study and for six weeks after the treatment. In addition, tanning is to be strictly avoided. Subjects should not receive any treatment with a laser or other devices in the study treatment area throughout the course of this study and follow-up examinations.

Protective eye goggles will be worn by both the patient and site staff performing the treatment for the duration of the treatment session.

### 7.3.2 ENROLLMENT/BASELINE

#### **Enrollment/Baseline Visit (Visit 1 – Day 1)**

Once a subject has been confirmed that they continue to meet inclusion/exclusion criteria, each subject will receive a unique identifying number that will be composed of a two-digit site number and a three digit subject number in sequence. This unique identifier will be used throughout the entire study and will be entered in the subject's case report form (CRF) and for each treatment.

#### **Treatment**

Based on the mild nature of treatment, anesthesia is not required. Treatment procedure should include positioning of the patient in a manner that enables access to the target treatment anatomical site. A water-based spray should be applied to the treatment area immediately prior to treatment.

Each subject will receive two consecutive treatments in the following order: the left flank of the abdomen will be treated with the diode laser device and the right flank of the abdomen will be treated with the LED device. The exact placement on the flank will be left to the principal investigator's judgement based on his assessment of individual subject requirements for treatment. Subjects will be treated on the same bilateral location with each device to ensure consistency of measurements. Both laser and LED applicators will be set to same output power level. Two levels will be used 41W (1.17W/cm^2) and 29W (0.83W/cm^2). The first level of 41W corresponds to initial heating for 4 minutes and the second level corresponds to duty cycle of 25 sec on and 10 sec off time. Total treatment time with each device will be 24 minutes (first 4 min at full power and next 16 min at duty cycle 25/10). Both device applicators have same output window dimensions and area 7x5 cm (35 cm^2). Both applicators are cooled by water chiller and therefore provided the same surface cooling temperature on skin.

Immediately (within 2 minutes) after treatment, 3 sterile thermocouple needles of different lengths (7-15 mm), will be inserted into the center of each applicator footprint. Temperature readings from each thermocouple needle will be recorded.

During treatment, subject reaction must be monitored and if the subjects verbally report an intolerable level of pain, treatment shall be ceased immediately.

The normal response to these treatments is transient erythema and edema. If any side effects occur other than a normal transient response, as indicated in the protocol, they will be recorded.

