## PROTOCOL SUMMARY

TITLE	Feasibility Study of a 950 nm Wavelength LED Device for Non-invasive Lipolysis of the Flanks
SUMMARY	Open-label, feasibility study comparing the tissue temperature profile of a 950 nm LED device and a 1060 nm diode laser for non-invasive lipolysis of the flanks. The study will enroll up to 10 subjects requesting non-invasive lipolysis of the flanks. Each subjects will receive a single treatment with each device on opposite flanks. Tissue temperatures in the treated areas will be recorded and compared.
OBJECTIVES	The objective of this clinical study is to compare the tissue temperature profiles of the LED device and diode laser device and to compare safety in the treatment of lipolysis of the flanks.
ENDPOINT	Primary objective 

• Temperature profile comparison at various tissue depths.

 Safety 

• Subject's assessment of discomfort and pain as measured by a 10 cm visual analog scale (VAS).

• Subjects experiencing a treatment-related adverse event (AE).

POPULATION	The study will enroll up to 10 male and female subjects, ≥ 18 years of age who are seeking non-invasive lipolysis of the flanks.
PHASE	Feasibility
NUMBER OF SITES	one
DESCRIPTION OF DEVICE	The investigational device uses LED technology. The 1060 nm diode laser has been approved by the FDA for non-invasive lipolysis of the flanks.
STUDY DURATION	Two months
PARTICIPANT DURATION	One day plus a telephone follow-up after one week

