## 4 STUDY DESIGN AND ENDPOINTS

### 4.1 DESCRIPTION OF THE STUDY DESIGN

This is an open-label, comparative, single-center study to evaluate the feasibility and safety of a LED device and a diode laser device for non-invasive lipolysis of the flanks.

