#### 4.2.1 PRIMARY ENDPOINTS

Tissue temperature profiles compared to the reference device.

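### Laser always first on the left flank and LED always second on the right: device is completely confounded with body side and treatment order in the primary comparison

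*Combined protocol and SAP*

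**What the plan says.** The Treatment part of section 7.3.2 gives each subject "two consecutive treatments in the following order: the left flank of the abdomen will be treated with the diode laser device", and then "the right flank of the abdomen will be treated with the LED device". The rule covers every subject and has no exception. The Protocol Summary is less specific, saying only that subjects "will receive a single treatment with each device on opposite flanks", and no other section randomises, alternates or balances side or order.

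Section 7.3.2 also says that "The exact placement on the flank will be left to the principal investigator's judgement", but requires matching locations on the two flanks. It sets the same output power for both applicators and describes the same window size and water cooling.

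Section 4.1 describes the trial as follows: "This is an open-label, comparative, single-center study". The primary endpoint in section 4.2.1 is "Tissue temperature profiles compared to the reference device". The General Approach under section 10.3 plans mean temperatures by device and thermocouple and the differences between them, without a side or order term. Section 10.4 gives no formal sample size calculation and a maximum of 10 subjects.

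**The concern.** Treating both flanks of one person removes differences between people. It does not remove differences between a person's left and right flanks, or between a first and a second session. If the assignment never varies, those differences are counted as part of the device effect.

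The protocol's own procedures make an order effect plausible:

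- **Pain.** The VAS is completed within 5 minutes of treatment and before any subsequent one. The LED rating therefore always comes from someone who has just had the laser and knows which device is which.
- **Temperature.** Section 7.3.2 does not say whether the needles go in after each treatment or after both. If after both, the laser flank has always had a whole LED session in which to cool. If after each, the LED pain score always follows needle insertion on the other flank.
- **Cooling.** The Post Treatment text allows cold packs straight after treatment, so the first flank could be cooled while the second is treated.

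Side effects could come from fat thickness, perfusion or operator access; the documents give no data on these. The investigator also chooses the placement already knowing which device goes on which side.

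At stake is the question in section 2.2: whether the LED heats tissue much as the reference device does. A side or order effect could create an apparent device difference or hide a real one, and nothing in the data would show it.

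**Working it through.** The plan states no power, significance level or effect size, so it has no figure to reproduce. The check is whether the device effect can be identified.

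**Inputs.** Assignment: laser left and first, LED right and second, for all subjects (7.3.2). Number of subjects: 10, the maximum (10.4). That the LED comes second is read from the treatments being consecutive and in a stated order.

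**Step 1: what the planned difference estimates.** For each subject,

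LED reading − laser reading = device effect + (right − left) + (second − first) + error.

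Every subject has the same signs on all three terms, so the mean difference estimates their sum.

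**Step 2: can a model separate them?** With 10 subjects there are 20 readings at a given depth. A model with 10 subject indicators plus device, side and order has 13 columns. Under the fixed assignment the last three columns are identical in all 20 rows, so the rank is 10 + 1 = 11. The device effect is not estimable once side and order effects are allowed.

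**Step 3: size of the bias.** The documents give no asymmetry or order figures. With a true device effect of 0 and assumed side-plus-order effects of 0.5, 1 or 2 °C, the expected LED − laser difference is 0.5, 1 or 2 °C, whatever the sample size.

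On a standardised scale, let d be the side-plus-order effect divided by the SD of the within-subject difference. A two-sided 5% paired t test with n = 10 has 9 df, critical value 2.262 and noncentrality d√10:

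| d (assumed) | d√10 | Probability of a nominally significant device difference |
|---|---|---|
| 0.25 | 0.79 | 0.109 |
| 0.50 | 1.58 | 0.293 |
| 0.75 | 2.37 | 0.562 |
| 1.00 | 3.16 | 0.803 |

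The protocol plans no test, so this table only illustrates scale.

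**Step 4: which layouts cure it.** With n = 10, subject effects and side and order terms fitted, the half-width is t(0.975, df) × √0.100, in units of the SD of the difference:

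| Layout | Rank (of 13) | Device estimable | df | 95% half-width |
|---|---|---|---|---|
| As written | 11 | No | – | – |
| Side balanced 5/5, order fixed | 12 | No | – | – |
| Order balanced 5/5, side fixed | 12 | No | – | – |
| Two linked sequences 5/5 (LED right and second; LED left and first) | 12 | Yes | 8 | 2.306 × 0.316 = 0.729 |
| Side crossed with order, 3/2/2/3 | 13 | Yes | 7 | 2.365 × 0.316 = 0.748 |

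A plain paired analysis under the current plan has half-width 2.262 × 0.316 = 0.715, but around the wrong quantity. The loss of precision is 0.729/0.715 = 1.02 for the linked layout and 0.748/0.715 = 1.05 for the crossed one.

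Balancing only side or only order is not enough. With both balanced, the signs cancel: for example, five differences shifted by +1 °C and five by −1 °C average to 0.

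**The case against.** The best defence accepts the confounding and disputes its weight.

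- **Confounding is not bias.** Bias needs a non-zero average side or order effect, and the documents give no evidence of one. This is fair: the size is unknown and could be small.
- **There are controls.** Matched location, power, window and cooling, and the requirement for bilateral fat, limit how different the two flanks can be. The first VAS is also protected from the second treatment. These controls narrow the plausible range, but none breaks the link between device and side or order.
- **Some mechanisms could be measured.** Fat thickness on each flank could be recorded and the paired difference adjusted for it. That is true of that component, but the protocol plans no such measurement and any constant side or order effect would remain.
- **Part of the aim does not need the contrast.** Whether LED readings reach the 42–47 °C range can be described from the right flank alone. This stands, although side and the preceding laser session could still affect those readings. The stated primary endpoint remains the comparison with the laser.
- **It is a descriptive feasibility study.** With no test and at most 10 subjects, false-positive rates do not describe a planned analysis. That is correct, and they are not the basis for the conclusion. A small sample gives imprecision, which an interval shows; a fixed assignment gives bias, which no interval shows.
- **A list for 10 may stop short.** Enrolment is up to 10, so early stopping can leave imbalance. Randomisation still removes systematic bias in expectation, and small blocks limit the imbalance.

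**Conclusion.** The concern holds and should be fixed before enrolment, because it cannot be repaired afterwards. Device, side and order are completely aliased in the contrast that is the primary endpoint and in the comparison of pain scores. This follows from the allocation rule alone and needs no assumption about variability.

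The size of the bias is unknown. It equals the sum of the average side and order effects and does not shrink with more subjects. The 0.5–2 °C and 0.25–1.0 SD values are assumptions used to show scale. As written, the study can attribute a difference, or a similarity, to the device only by assuming no net side-plus-order effect, and its data cannot test that assumption.

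**What to change.** Replace the fixed assignment in section 7.3.2 with a list prepared in advance that randomises which device goes on which flank and, separately, which is used first.

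- **Layout.** Use the four combinations of side and order in the numbers 3/2/2/3 over 10 subjects, so that the laser is on the left in 3 + 2 = 5 and first in 3 + 2 = 5. Because enrolment may stop early, build the list as two blocks of four (each combination once) and a final pair that are opposite in both side and order. Side and order are then balanced after 4, 8 and 10 subjects.
- **Placement.** Mark both mirrored footprints before opening the subject's sealed envelope. The envelope does not blind anyone; it keeps the placement choice independent of the device.
- **Analysis.** In the General Approach under section 10.3, state that the LED − laser difference is estimated within subject at each depth, with side and order balanced by design or included as terms. Record side and order on the CRF.
- **Needle timing.** State whether temperatures are read after each treatment or after both, so that the order effect has a defined meaning.

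The cost is a few sentences in each section, a 10-line list and one CRF field. No subjects, visits or procedures are added and no device setting changes. Staff must check the assignment before each session, and fitting both terms widens the interval by about 5%.

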### 2.2 RATIONALE

A new emerging technology in the area of aesthetic medicals device is LED (light-emitting diode) photo-modulation. It is currently being used to stimulate fibroblasts to produce collagen and to destroy bacteria on the skin. In this study, a 950 nm LED investigational device is being evaluated to determine if it is able to target adipocytes by maintaining a controlled temperature of 42-47 °C, similar to the reference device. In addition, the safety of the LED device will be compared to the reference device.

The use of this LED device has been determined to present non-significant risk for the intended use in this study, because the device is not:

- Intended as an implant and presents a potential for serious risk to the health, safety, or welfare of a subject;
- Is purported or represented to be for use supporting or sustaining human life and presents a potential for serious risk to the health, safety, or welfare of a subject;
- Is for a use of substantial importance in diagnosing, curing, mitigating, or treating disease, or otherwise preventing impairment of human health and presents a potential for serious risk to the health, safety, or welfare of a subject; or
- Otherwise presents a potential for serious risk to the health, safety, or welfare of a subject.

This study will be conducted in compliance with the protocol and according to Good Clinical Practice standards.

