### 10.3 DESCRIPTION OF STATISTICAL METHODS

#### 10.4.1 GENERAL APPROACH

This is an open-label, comparative feasibility study of an investigational LED device and a diode laser device for non-invasive lipolysis of the flanks.

Mean temperature reading from each device and each thermocouple will be calculated and temperature differences will be determined.

The safety analysis will be done by analyzing spontaneous reports of adverse events (AE), subjects' completed 10 cm discomfort/pain VAS and short term response reports by the principal investigator from his/her observation/examination of the treated area. Appropriate Medical Dictionary for Regulatory Activities (MedDRA) code will be used to describe all spontaneously reported or other study related adverse events.

Summaries of spontaneously reported or other study related adverse events will be presented as:

- Number (%) of subjects with any AE,
- Number (%) of subjects with any serious adverse events (SAE),
- Number (%) of subjects permanently withdrawn from treatment due to AE

Summaries of analysis of immediate and short term response reports by the principal investigator examination will be displayed on a bar or pie chart as;

- the overall frequency of subjects with each event (pain during treatment, hemorrhage, burn, erythema, edema, purpura)
- Frequency of subjects with specific severity/intensity for each event using a 5 points scale: 1=none; 2=trace; 3=moderate; 4=marked; 5=severe
- The overall percentage or proportion of subject observed with marked or severe intensity of any event will be calculated and compared to those with none, trace or moderate severity/intensity with the aid of a bar or pie chart.

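### The stated 24-minute treatment time per device does not match its own phases, which add up to 20 minutes, so the exposure behind the tissue temperatures is not fixed.

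*Combined protocol and SAP*

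**What the plan says.** The schedule is in section 7.3.2 under Treatment and applies to both devices. On the first phase: "The first level of 41W corresponds to initial heating for 4 minutes". On the second, run at 29 W: "the second level corresponds to duty cycle of 25 sec on and 10 sec off time". The durations are then put together: "Total treatment time with each device will be 24 minutes (first 4 min at full power and next 16 min at duty cycle 25/10". Both applicators have a 35 cm² window and are to be set to the same output power.

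Section 6.1.2 gives the LED session length separately: "The duration of exposure and frequency of exposure to the LED will be one 24 minute session".

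Temperature is read from three thermocouple needles inserted within 2 minutes after treatment. Section 2.2 says the study is to determine whether the LED is "able to target adipocytes by maintaining a controlled temperature of 42-47 °C, similar to the reference device". The analysis, in section 10.3 under General Approach, is: "Mean temperature reading from each device and each thermocouple will be calculated and temperature differences will be determined".

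**The concern.** The total and its parts disagree within one sentence. Each side has support elsewhere: the 4-minute initial phase appears twice in section 7.3.2, and the 24-minute total reappears in section 6.1.2. The documents do not show which figure is wrong, and they mention no pause, pre-cooling or post-cooling that would fill 4 minutes.

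Exposure time is part of the intervention itself. The per-device temperatures, and the thermal load behind the VAS scores and the burn, erythema and edema grades, depend on it. An operator who follows the phases breaches the total, and the reverse. A monitor applying section 14.3 could not tell a deviation from compliance. If run time differed between subjects but matched within each subject, the LED-laser comparison would stay at equal exposure, but each device's mean would mix two exposures. With at most 10 subjects, a few differing run times would matter for those means.

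**Working it through.** **Inputs, all from section 7.3.2 (Treatment) except the last**

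- Stated total: 24 min per device
- Phase 1: 4 min at 41 W
- Phase 2: 16 min, 25 s on and 10 s off, at 29 W
- Window area: 35 cm²
- Section 6.1.2: 24 min for the LED

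**1. Power densities.** 41/35 = 1.17 and 29/35 = 0.83 W/cm². Both stated values are reproduced, so the power and area figures agree with each other.

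**2. Total time.** 4 + 16 = 20 min. The stated 24 min is not reproduced. The gap is 4 min: 4/20 = 20% of the summed phases, 4/24 = 16.7% of the stated total.

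**3. Can the duty cycle close the gap?** One cycle is 35 s, with an on-fraction of 25/35.

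- If 16 min is on-time only, the clock time is 16 × 35/25 = 22.4 min and the total is 4 + 22.4 = 26.4 min, not 24.
- If cycling fills the remaining 24 − 4 = 20 min, on-time is 20 × 25/35 = 14.3 min, not 16.

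Neither reading gives 24 min together with 4 and 16.

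**4. What does 29 W mean?** The text does not say whether it is the power during the 25 s on-phase or the average over the cycle. Since 41 × 25/35 = 29.3 W, the second reading is as open as the first.

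**5. Delivered energy.** Phase 1 gives 41 × 240 s = 9,840 J. Phase 2 gives 29 × (25/35) × seconds if 29 W is on-phase power, or 29 × seconds if it is the time average. The table places the missing 4 min in the duty-cycle phase, so phase 2 lasts 960 s or 1,200 s.

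| Meaning of 29 W | 20 min | 24 min | Difference | On 20-min base | On 24-min base |
|---|---|---|---|---|---|
| On-phase power | 29,726 J (849 J/cm²) | 34,697 J (991 J/cm²) | 4,971 J | 16.7% | 14.3% |
| Time average | 37,680 J | 44,640 J | 6,960 J | 18.5% | 15.6% |

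Other placements of the missing 4 min:

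- Unpowered: no change in energy. If this time came at the end, the temperature reading could fall up to 4 + 2 = 6 min after the last energy delivery.
- At 41 W: +9,840 J, which is 9,840/29,726 = 33.1% or 9,840/37,680 = 26.1% of the 20-min energy. This contradicts the twice-stated 4 min at full power and is the placement the text supports least.

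The documents give no way to turn joules into degrees, so no temperature change is claimed.

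**The case against.** The strongest objection is to the weight of the point. The primary endpoint is a comparison with the reference device, and section 7.3.2 gives both devices the same schedule, power levels and window. Nothing in the documents plans different run times for the two flanks. This stands: as planned, the paired difference is not biased.

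The 42-47 °C range appears as rationale only. Section 10 has no threshold analysis or success criterion that uses it, and readings taken after treatment could not show that a temperature was maintained during it, whatever the duration. This also stands, and it limits how much can rest on that target. It does not remove the dependence of the reported per-device means on exposure.

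With one site and sponsor training before any treatment, run time may in practice be the same for every subject. That is possible, but training does not correct the text, and a consistent choice would still breach one part of the sentence.

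The meaning of 29 W is a separate ambiguity and does not cause the 20-versus-24-minute mismatch. That is right. It is included because the energy cannot be stated without it.

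**Conclusion.** The concern holds. The protocol's 24-minute total does not equal its stated phases of 4 and 16 minutes, and no reading of the duty cycle reconciles them. The 4-minute gap follows directly from the text and needs no assumption.

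The energy consequence is conditional. If the missing time is spent cycling, it is 16.7% (29 W as on-phase power) or 18.5% (29 W as time average) of the 20-minute energy. It is zero if that time is unpowered. Taking both ambiguities together, the four totals in the table run from 29,726 to 44,640 J, and 44,640/29,726 = 1.50.

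What is affected is the absolute temperature for each device, the safety outcomes and the reproducibility of the treatment. The LED-laser difference is affected only if the two flanks of one subject are run for different times. Because this is a wrong operative figure and not a missing detail, it must be corrected.

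**What to change.** The sponsor and investigator should reconcile section 7.3.2 (Treatment) with section 6.1.2 so that the phase durations add up to the stated total for both devices. If part of the session is unpowered, its place in the sequence should be stated. The same correction should say whether 29 W is the power during the on-phase or the average over the cycle. This review does not say which duration or power reading is right.

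Actual start and stop times for each flank should also be on the CRF, if they are not there already (the CRFs are not among the documents). Equal exposure within each subject could then be verified, and any variation between subjects would be visible when the per-device means are read.

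The cost is about one corrected sentence in 7.3.2, a check of 6.1.2 against it, IRB review of the amendment as section 13.2 requires, and a start and a stop time field per flank.
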